10.1. Appendix 1: Regulatory, Ethical, and Study Oversight Considerations

10.1.1. Regulatory and Ethical Considerations

This study will be conducted in accordance with the protocol and with the following:

- consensus ethical principles derived from international guidelines, including the Declaration of Helsinki and Council for International Organizations of Medical Sciences (CIOMS) International Ethical Guidelines
- applicable ICH GCP Guidelines, and
- applicable laws and regulations.

The protocol, protocol amendments, ICF, Investigator Brochure, and other relevant documents, for example, advertisements, must be submitted to an IRB/IEC by the investigator and reviewed and approved by the IRB/IEC before the study is initiated.

Any amendments to the protocol will require IRB/IEC approval before implementation of changes made to the study design, except for changes necessary to eliminate an immediate hazard to study participants.

Protocols and any substantial amendments to the protocol will require health authority approval prior to initiation except for changes necessary to eliminate an immediate hazard to study participants.

The investigator will be responsible for

- providing written summaries of the status of the study to the IRB/IEC annually or more frequently in accordance with the requirements, policies, and procedures established by the IRB/IEC
- notifying the IRB/IEC of SAEs or other significant safety findings as required by IRB/IEC procedures
- providing oversight of study conduct for participants under their responsibility and adherence to requirements of 21 CFR, ICH guidelines, the IRB/IEC, European Regulation 536/2014 for clinical studies (if applicable), and all other applicable local regulations, and
- reporting to the sponsor or designee significant issues related to participant safety, participant rights, or data integrity.

Investigator sites are compensated for participation in the study as detailed in the Clinical Trial Agreement.

10.1.2. Financial Disclosure

Investigators and sub-investigators will provide the sponsor with sufficient, accurate financial information as requested to allow the sponsor to submit complete and accurate financial certification or disclosure statements to the appropriate regulatory authorities. Investigators are

responsible for providing information on financial interests during the course of the study and for 1 year after completion of the study.

10.1.3. Informed Consent Process

The investigator or the investigator's representative will explain the nature of the study, including the risks and benefits, to the potential participant and, if applicable, the potential participant's legally authorized representative and answer all questions regarding the study.

Potential participants must be informed that their participation is voluntary. Participants and, if applicable, their legally authorized representative will be required to sign a statement of informed consent that meets the requirements of 21 CFR 50, local regulations, ICH guidelines, privacy and data protection requirements, where applicable, and the IRB/IEC or study center.

The medical record must include a statement that written informed consent was obtained before the participant was entered in the study and the date the written consent was obtained. The authorized person obtaining the informed consent must also sign the ICF.

Revised consents must be appropriately obtained using the correct approved ICFs for applicable study participants in accordance with sponsor and ERB consenting guidance.

A copy of the ICF(s) must be provided to the participant and, if applicable, the participant's legally authorized representative, and is kept on file.

Participants who are rescreened are required to sign a new ICF.

10.1.4. Data Protection

Participants will be assigned a unique identifier by the sponsor to protect the participant's personal data. Any participant information, such as records, datasets, or tissue samples that are transferred to the sponsor, will contain the identifier only. Participant names or any information which would make the participant identifiable will not be transferred.

The participant must be informed that the participant's personal study-related data will be used by the sponsor in accordance with local data protection law. The level of disclosure must also be explained to the participant who will be required to give consent for their data to be used as described in the informed consent. This is done by the site personnel through the informed consent process.

The participant must be informed through the informed consent by the site personnel that their medical records may be examined by Clinical Quality Assurance auditors or other authorized personnel appointed by the sponsor, by appropriate IRB/IEC members, and by inspectors from regulatory authorities.

The sponsor has processes in place to ensure information security, data integrity, and data protection. These processes address management of data transfer, and prevention and management of unauthorized access, disclosure, dissemination, alteration, or loss of information or personal data. These processes include appropriate contingency plan(s) for appropriate and timely response in the event of a data security breach.

The transfer of personal data is subject to appropriate safeguards through contractual agreements and processes. The sponsor's processes are compliant with local privacy laws and relevant legislations, including the General Data Protection Regulation (GDPR).

10.1.5. Committees Structure

An AC internal to Lilly will review safety and efficacy data during the study.

The AC will be fully independent from the study team and will include, at a minimum, a Lilly medical physician and a statistician.

Details about the AC membership, purpose, responsibilities, and operation will be described in an AC charter, which will be approved before first participant visit.

Study sites will receive information about interim results ONLY if they need to know for the safety of their participants. The AC will determine whether there are sufficient safety concerns to justify a change in the conduct of the study or the termination of study treatment or enrollment.

10.1.6. Dissemination of Clinical Study Data

Reports

The sponsor will disclose a summary of study information, including tabular study results, on publicly available websites where required by local law or regulation.

The summary of results will be posted within the time frame specified by local law or regulation. If the study remains ongoing in some countries and a statistical analysis of an incomplete dataset would result in analyses lacking scientific rigor (for example, underpowered) or compromise the integrity of the overall analyses (for example, trial not yet unblinded), the summary of results will be submitted within 1 year after the end of the study globally or as soon as available, whichever is earlier.

Data

The sponsor provides access to all individual participant data collected during the trial, after anonymization, with the exception of pharmacokinetic or genetic data.

Data are available to request 6 months after the indication studied has been approved in the US and EU and after primary publication acceptance, whichever is later. No expiration date of data requests is currently set once data are made available.

Access is provided after a proposal has been approved by an independent review committee identified for this purpose and after receipt of a signed data-sharing agreement.

Data and documents, including the study protocol, statistical analysis plan, clinical study report, and blank or annotated case report forms, will be provided in a secure data-sharing environment for up to 2 years per proposal.

For details on submitting a request, see the instructions provided at **CCI** .

10.1.7. Data Quality Assurance

All participant data relating to the study will be recorded on printed or electronic CRFs unless transmitted to the sponsor or designee electronically, for example, laboratory data. The investigator is responsible for verifying that data entries are accurate and correct by physically or electronically signing the CRF.

The investigator must maintain accurate documentation (source data) that supports the information entered in the CRF. This includes laboratory tests, medical records, and clinical notes.

The investigator must review and confirm that data entries are accurate and complete throughout the duration of the study, by physically or electronically signing the CRF, as instructed by the sponsor. All completed CRFs must be signed prior to archival.

The investigator must permit study-related monitoring, audits, IRB/IEC review, and regulatory agency inspections and provide direct or remote access to source documents.

Quality tolerance limits will be predefined to identify systematic issues that can impact participant safety and/or reliability of study results. These predefined parameters will be monitored during the study and important excursions from the quality tolerance limits and remedial actions taken will be summarized in the clinical study report.

Monitoring details describing strategy, for example, risk-based initiatives in operations and quality, such as risk management and mitigation strategies and analytical risk-based monitoring, methods, responsibilities and requirements, including handling of noncompliance issues and monitoring techniques are provided in the Monitoring Plan.

The sponsor or designee is responsible for the data management of this study, including quality checking of the data.

The sponsor assumes accountability for actions delegated to other individuals, for example, contract research organizations.

The sponsor or designee will perform monitoring to confirm that data transcribed into the CRF by authorized site personnel are accurate, complete, and verifiable from source documents; that the safety and rights of participants are being protected; and that the study is being conducted in accordance with the currently approved protocol and any other study agreements, ICH GCP, and all applicable regulatory requirements.

Records and documents, including signed ICFs, pertaining to the conduct of this study must be retained by the investigator for the time period outlined in the Clinical Trial Agreement unless local regulations or institutional policies require a longer retention period. No records may be destroyed during the retention period without the written approval of the sponsor. No records may be transferred to another location or party without written notification to the sponsor.

In addition, the sponsor or its representatives will periodically check a sample of the participant data recorded against source documents at the study site. The study may be audited by the sponsor or its representatives, or regulatory agencies at any time. Investigators will be given notice before an audit occurs.

Data capture system

The investigator is responsible for ensuring the accuracy, completeness, legibility, and timeliness of the data reported to the sponsor.

An EDC will be used in this study for the collection of CRF data. The investigator maintains a separate source for the data entered by the investigator or designee into the sponsor-provided EDC system. The investigator is responsible for the identification of any data to be considered source and for the confirmation that data reported are accurate and complete by signing the CRF.

Data collected via the sponsor-provided data capture system(s) will be stored at third party. The investigator will have continuous access to the data during the study and until decommissioning of the data capture system. Prior to decommissioning, the investigator will receive or access an archival copy of pertinent data for retention.

Data managed by a central vendor, such as laboratory test data, will be stored electronically in the central vendor's database system and reports will be provided to the investigator for review and retention. Data will subsequently be transferred from the central vendor to the sponsor data warehouse.

Data from complaint forms submitted to the sponsor will be encoded and stored in the global product complaint management system.

10.1.8. Source Documents

Source documents provide evidence for the existence of the participant and substantiate the integrity of the data collected. Source documents are filed at the investigator's site.

Data reported on or entered in the CRF and are transcribed from source documents must be consistent with the source documents or the discrepancies must be explained. The investigator may need to request previous medical records or transfer records, depending on the study. Also, current medical records must be available.

Definition of what constitutes source data can be found in the site confirmation of source data.

10.1.9. Study and Site Start and Closure

Study start

The study start date is the date on which the clinical study will be open for recruitment of participants.

First act of recruitment

The first act of recruitment is the opening of the first site.

Study or site termination

The sponsor or sponsor's designee reserves the right to close the study site or terminate the study at any time for any reason at the sole discretion of the sponsor. Study sites will be closed upon study completion. A study site is considered closed when all required documents and study supplies have been collected and a study-site closure visit has been performed.

The investigator may initiate study-site closure at any time, provided there is reasonable cause and sufficient notice is given in advance of the intended termination.

Reasons for the early closure of a study site by the sponsor or investigator may include but are not limited to

- for study termination due to discontinuation of further study intervention development
- for site termination due to
 - failure of the investigator to comply with the protocol, the requirements of the IRB/IEC or local health authorities, the sponsor's procedures, or GCP guidelines
 - inadequate recruitment, evaluated after a reasonable amount of time of participants by the investigator, or
 - total number of participants included earlier than expected.

If the study is prematurely terminated or suspended, the sponsor shall promptly inform the investigators, the IECs/IRBs, the regulatory authorities, and any contract research organization(s) used in the study of the reason for termination or suspension, as specified by the applicable regulatory requirements. The investigator shall promptly inform the participant and should assure appropriate participant therapy and/or follow-up.

10.1.10. Publication Policy

In accordance with the sponsor's publication policy, the results of this study will be submitted for publication by a peer-reviewed journal.

10.1.11. Investigator Information

Researchers with appropriate education, training, and experience, as determined by the sponsor, will participate as investigators in this clinical trial.

10.1.12. Sample Retention

Sample retention enables use of new technologies, response to regulatory questions, and investigation of variable response that may not be observed until later in the development of pirtobrutinib.

Sample Type	Custodian	Maximum Retention Period after Last Participant Visit^a
Pharmacokinetics	Sponsor or designee	1 year
Biomarkers	Sponsor or designee	15 years

^a Sample retention periods may differ dependent upon local regulations.

10.2. Appendix 2: Clinical Laboratory Tests

The tests detailed in the table below will be performed by the local laboratory or a Lilly-designated laboratory.

In circumstances where the sponsor approves local laboratory testing in lieu of central laboratory testing, the local laboratory must be qualified in accordance with applicable local regulations.

Additional tests may be performed at any time during the study as determined necessary by the investigator or required by local regulations.

Investigators must document their review of the laboratory safety results.

Clinical Laboratory Tests	Comments
Hematology	Locally performed
Hemoglobin	
Hematocrit	
Erythrocyte count (RBCs - red blood cells)	
Leukocytes (WBCs - white blood cells)	
Differential	
Percent and/or absolute count of:	
Neutrophils	Neutrophils reported by automated differential hematology instruments may include both segmented and band forms. When a manual differential is needed to report the neutrophils, the segmented and band forms should be added together and recorded on the CRF
Lymphocytes	
Monocytes	
Eosinophils	
Basophils	
Platelets	
Coagulation	Locally performed
International normalized ratio (INR) or prothrombin time (PT)	
Activated partial thromboplastin time (aPTT) or PTT	
Clinical chemistry	Locally performed
Sodium	
Potassium	
Chloride	
Blood urea nitrogen (BUN) or blood urea	
Creatinine	
Creatine kinase (CK)	
Alkaline phosphatase (ALP)	
Alanine aminotransferase (ALT)	
Aspartate aminotransferase (AST)	
Total bilirubin	

Clinical Laboratory Tests	Comments
Direct bilirubin	
Total protein	
Albumin	
Calcium (serum)	
Magnesium	
Phosphorus	
Uric acid	
Lactate dehydrogenase (LDH)	
Glucose (random)	
Urinalysis	Locally performed
Specific gravity	
pH	
Protein	
Glucose	
Ketones	
Bilirubin	
Urobilinogen	
Blood	
Nitrite	
Urine leukocyte esterase	Urine microscopy may be used in the place of the urine leukocyte esterase assessment to test for the presence of WBCs
Microscopic examination of sediment	If clinically indicated
Pregnancy test	Locally performed
Serum pregnancy	For participants of childbearing potential
Urine pregnancy	For participants of childbearing potential
Hepatitis serology and CMV	Locally performed
Hepatitis B Virus (HBV) testing	All participants should have serology, including hepatitis B surface antigen and hepatitis B core total antibody or an HBV DNA
HBV DNA	Collect only if necessary to determine eligibility as per Section 5.2
Hepatitis C Virus (HCV) testing	
CMV PCR	
Pharmacokinetic samples pirtobrutinib concentration	Assayed by Lilly-designated laboratory. Results will not be provided to the investigative sites
Immunoglobulin panel	Locally performed
IgA	
IgE	
IgG	
IgM	

10.3. Appendix 3: Adverse Events and Serious Adverse Events: Definitions and Procedures for Recording, Evaluating, Follow-Up, and Reporting

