HCV	X						If HCV antibody test is positive, it must be followed by an HCV RNA test. See Section 5.2.
HBV	X	X					See Sections 5.2 and 8.2.7 for details.
CMV PCR	X						
Immunoglobulin panel	X						
Coagulation panel	X	X					After screening: As clinically indicated.

Study JZNX	Screening	Study Treatment Cycle = 28 days			Posttreatment		Instructions
Cycle/Visit	Baseline (Day Relative to C1D1)	Cycles 1-6	Cycles 7-24	Cycles 25+	Short- Term Follow-Up (STFU)	Long- Term Follow- Up ^{††} (LTFU)	Cycles 1-6: visits occur at each cycle. Cycles 7-24: visits occur Q16W at C9, C13, C17, C21, and C25. Cycles 25+: visits occur Q24W. ^{††} Occurs every 16 weeks for first 2 years relative to C1D1, and then every 24 weeks.
Day of cycle or visit		Day 1	Day 1	Day 1	V801	V802-8XX	
Visit window (days)	Up to 28	± 7	± 14	± 14	28 + 7	±14	C1D1: see visit window instructions in Section 1.3.
Pregnancy test (serum or urine)	X	X			X		Collect for individuals of childbearing potential. See Section 10.4 for definitions. Screening: Serum sample preferred. C1D1: Perform within 24 hr before the first dose of pirtobrutinib. At any time during the study: monthly or as required per local regulations or institutional guidelines. STFU: Serum sample preferred.
Bone marrow biopsy		X					Only collect and evaluate locally to confirm CR or disease progression due to cytopenia. See Section 8.1.3.
CCI							
Stored samples							
CCI							
Randomization, dosing, dosing diary, and IWRS							
Register visit with IWRS	X	X	X	X	X		Visits are C1-6, C9, C13, C17, C21, C25, and then Q24W.
Randomization via IWRS	X						Upon confirmation of eligibility.
Dispense pirtobrutinib		X	X	X			Dosing is oral daily (continuous).
Dispense participant dosing diary		X					

Study JZNX	Screening	Study Treatment Cycle = 28 days			Posttreatment		Instructions
Cycle/Visit	Baseline (Day Relative to C1D1)	Cycles 1-6	Cycles 7-24	Cycles 25+	Short- Term Follow-Up (STFU)	Long- Term Follow- Up ^{††} (LTFU)	Cycles 1-6: visits occur at each cycle. Cycles 7-24: visits occur Q16W at C9, C13, C17, C21, and C25. Cycles 25+: visits occur Q24W. ^{††} Occurs every 16 weeks for first 2 years relative to C1D1, and then every 24 weeks.
Day of cycle or visit		Day 1	Day 1	Day 1	V801	V802-8XX	
Visit window (days)	Up to 28	± 7	± 14	± 14	28 + 7	±14	C1D1: see visit window instructions in Section 1.3.
Participant returns dosing diary for site review		X					
Assess dosing compliance		X	X	X			
Participant status							
Survival status		X					

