5.2. Exclusion Criteria

Participants are excluded from the study if any of the following criteria applies:

Medical conditions

14. Have known or suspected Richter's transformation to diffuse large B-cell lymphoma, prolymphocytic leukemia, or Hodgkin's lymphoma at any time before randomization.
15. Have known or suspected history of central nervous system involvement by CLL/SLL.
16. Previous or concurrent cancer distinct from CLL/SLL within 3 years before randomization. Exceptions may occur with documented sponsor approval. Examples include
 - nonmelanoma skin cancer or lentigo maligna melanoma
 - cervical carcinoma in situ
 - localized prostate cancer undergoing active surveillance, and
 - localized (for example, lymph node negative) breast cancer with no evidence of active disease present for more than 3 years. Individual may be receiving adjuvant hormonal therapy.

17. Have a history of \geq Grade 3 bleeding due to treatment with a BTK inhibitor.
18. Have major surgery planned within 4 weeks of planned first dose of study intervention.
19. Have ongoing drug-induced liver injury, primary biliary cirrhosis, or extrahepatic obstruction caused by cholelithiasis, or cirrhosis of the liver.
20. Have significant cardiovascular disease defined as any of the following:
 - a. unstable angina or acute coronary syndrome within the past 2 months before randomization
 - b. history of myocardial infarction within 3 months before randomization
 - c. documented LVEF by any method of $\leq 40\%$ within the 12 months before randomization
Exception – individual has ≥ 2 subsequent measurements of any kind, separated by a minimum of 3 weeks, that documents LVEF recovery $>40\%$
 - d. \geq Grade 3 New York Heart Association functional classification system of heart failure, or
 - e. uncontrolled or symptomatic arrhythmias.
21. Have a QTc prolongation using Fridericia's formula (QTcF) >470 ms. See Section 8.2.3 for details and potential corrections.
22. Have hepatitis B testing results at screening indicating active infection defined as positive for HBsAg or PCR positive for HBV DNA.
Exception - Individuals with negative HBsAg and positive anti-HBc if HBV DNA is negative before randomization.
23. Have HCV defined as positive for anti-HCV antibodies.
Exception - Individuals positive for anti-HCV antibodies and negative for HCV RNA before randomization.
24. Have known active CMV infection as determined through CMV PCR testing.

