8.2.4. Clinical Safety Laboratory Tests

See Section 10.2 for the list of clinical laboratory tests to be performed and the SoA for the timing and frequency.

The investigator must review the laboratory results, document this review, and report any clinically relevant changes occurring during the study as an AE. The laboratory results must be retained with source documents unless a Source Document Agreement or comparable document cites an electronic location that accommodates the expected retention duration.

Clinically significant abnormal laboratory findings are those which are not associated with the underlying disease, unless judged by the investigator to be more severe than expected for the participant's condition.

All laboratory tests with values considered clinically significantly abnormal during participation in the study or within 7 days after the last dose of study intervention should be repeated until the values return to normal or baseline or are no longer considered clinically significant by the investigator or medical monitor.

If such values do not return to normal/baseline within a period of time judged reasonable by the investigator, the etiology should be identified and the sponsor notified.

All protocol-required laboratory assessments, as defined in Section 10.2, must be conducted in accordance with the SoA, standard collection requirements, and laboratory manual.

If laboratory values from non-protocol-specified laboratory assessments performed at an investigator-designated local laboratory require a change in participant management or are considered clinically significant by the investigator, for example, SAE or AE or dose modification, then report the information as an AE.

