8.2.7. Hepatitis B Virus Monitoring for Reactivation in High-Risk Patients

See Section 5.2 for enrollment criteria.

Individuals enrolled with positive anti-HBc and negative HBsAg and HBV DNA should undergo regular monitoring for viral reactivation by performing testing for HBV DNA by PCR approximately every 2-4 months throughout the study and at 6 months after short-term follow-up.

If HBV DNA becomes positive, consider withholding pirtobrutinib and consulting with a hepatologist or gastroenterologist for further assessment.

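### Appendix 2 limits HBV DNA testing to eligibility, which contradicts the on-study reactivation monitoring in Section 8.2.7 (minor, participant safety)

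*Supplement*

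**What the plan says.** Four places in the protocol bear on HBV DNA testing.

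- **Section 5.2, criterion 22.** Active hepatitis B excludes, with one exception: "Individuals with negative HBsAg and positive anti-HBc if HBV DNA is negative before randomization". Such people may enrol.
- **Section 8.2.7.** This section covers the same people after enrolment. They should be monitored for viral reactivation by "performing testing for HBV DNA by PCR approximately every 2-4 months throughout the study and at 6 months after short-term follow-up". It then gives the action: "If HBV DNA becomes positive, consider withholding pirtobrutinib and consulting with a hepatologist or gastroenterologist for further assessment".
- **Section 1.3.1, SoA.** The HBV row is marked at screening and once more, with the instruction "See Sections 5.2 and 8.2.7 for details".
- **Section 10.2, Appendix 2.** The comment beside HBV DNA reads "Collect only if necessary to determine eligibility as per Section 5.2".

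Section 8.2.4 sets the roles of the last two: "See Section 10.2 for the list of clinical laboratory tests to be performed and the SoA for the timing and frequency".

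**The concern.** The monitoring in Section 8.2.7 takes place after eligibility has been settled. A comment that confines HBV DNA to settling eligibility therefore excludes every test that Section 8.2.7 asks for. Appendix 2 is not background text: Section 8.2.4 makes it the list of what is performed. Other entries in its comments column also act as collection conditions, for example urine sediment microscopy only where clinically indicated and pregnancy tests only for those of childbearing potential. Site staff who build a laboratory order set from that table could reasonably take the HBV DNA comment as an instruction.

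At stake is a safety check in a group that the title of Section 8.2.7 calls high-risk. If the PCR is not drawn, nothing prompts the investigator to consider a hold or a referral on virological grounds.

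**Working it through.** There is no plan figure to reproduce and no formula to apply. The check compares the texts.

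**1. Is it the same test in the same people?** Yes. Criterion 22 admits people with positive anti-HBc, negative HBsAg and negative HBV DNA, and Section 8.2.7 names that same group. Both Section 8.2.7 and Appendix 2 refer to HBV DNA.

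**2. Can both instructions be followed?** No. Section 8.2.7 asks for HBV DNA during the study and after treatment. Appendix 2 allows it for one purpose, which is complete before randomization. Its wording is not limited to the screening visit and does not mention Section 8.2.7.

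**3. Which text governs?** Section 8.2.4 leaves timing and frequency to the SoA, and the SoA's HBV row refers to Section 8.2.7. That section is specific: it gives the population, assay, interval, post-treatment test and response to a positive result. So the Appendix 2 comment is the one out of line. The column span of the second SoA mark cannot be read from the extracted table. The argument rests on the cross-reference, not on that mark.

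**4. Do other provisions restore the schedule?**

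| Provision | What it does | Restores scheduled HBV DNA? |
|---|---|---|
| Appendix 2: "Additional tests may be performed at any time during the study as determined necessary by the investigator" | Permits a test at discretion | No; it sets no interval |
| Section 8.2.4: "The investigator must review the laboratory results, document this review" | Acts on results in hand | No; it cannot act on a sample not drawn |
| Section 8.2.6, hepatic work-up | Includes hepatitis B serology if a defined liver-test abnormality persists or worsens | No; it needs an abnormal liver test first |
| Appendix 5, liver panel | Lists HBV DNA, footnoted as reflex or confirmatory and dependent on regulatory requirements or availability | No; same trigger, and conditional |

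The Section 8.2.6 trigger, for a participant whose baseline ALT or AST is below 1.5 times ULN, is ALT or AST of at least 5 times ULN, or at least 3 times ULN with total bilirubin of at least 2 times ULN. Higher baselines have their own thresholds, relative to baseline.

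**5. How often are liver enzymes drawn?** Using 365/12 = 30.4 days per month:

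- Cycles 1-6: every 28 days, so more often than every 2-4 months.
- Cycle 9 to Cycle 25: every 16 weeks; 16 × 7 = 112 days; 112/30.4 = 3.7 months, inside the 2-4 month range.
- After Cycle 25: every 24 weeks; 24 × 7 = 168 days; 168/30.4 = 5.5 months, outside that range.

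The chemistry row shows no mark for long-term follow-up, as far as the extracted table can be read. Chemistry is thus a real backup, and a frequent one early on. It is a different test, however, and leads to hepatitis testing only after the trigger in step 4.

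**The case against.** The strongest reply is that the protocol already resolves the conflict. Timing belongs to the SoA, the SoA refers to Section 8.2.7, and Section 8.2.7 is explicit. The comment also has a natural screening reading. The Appendix 2 row above it asks all participants for hepatitis B serology or an HBV DNA, and the next row may be meant only to avoid PCR in people whose eligibility does not depend on it. On this view one table cell is untidy and nobody is misled.

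Much of this stands. It is why the point is minor and why most sites would be expected to test. It does not reconcile the texts: the comment is worded as an exclusive condition, in the table to which Section 8.2.4 sends sites for the list of tests.

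Three further points for the other side also stand:

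- Section 8.2.7 says that monitoring should be done, and a positive result asks the investigator to consider a hold. Neither is an absolute mandate.
- ALT and AST are drawn every 28 days in Cycles 1-6, and once the hepatic work-up is triggered, hepatitis B serology is part of its minimum content. A reader might infer that this route would detect reactivation later than scheduled PCR. The documents say nothing on the relative timing, so that inference is not part of this point.
- A reader might turn the 2-4 month interval into a number of tests lost per participant. That would only restate the interval for an assumed treatment time. The test due 6 months after short-term follow-up may also fall after the study has ended, since Section 4.4 closes it once data for the final primary analysis are available.

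**Conclusion.** The Appendix 2 comment is wrong as written and should be corrected. It is a minor inconsistency that concerns participant safety. The conclusion rests on the current wording of Sections 5.2, 8.2.4, 8.2.7 and 10.2 and on the SoA cross-reference, and needs no outside figure.

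Its practical size is unknown. It depends on how many participants enrol under the criterion 22 exception and on whether any site follows the comment in place of Section 8.2.7. The documents give neither, and no estimate is offered.

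A reader might infer that the protocol has withdrawn reactivation monitoring. The documents do not support that: the dedicated section and the SoA both keep it. Nor does the inconsistency bear on the ORR analysis or the comparison between doses.

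**What to change.** In the HBV DNA row of Appendix 2, strike the word *only* and add at the end of the comment: *, and for reactivation monitoring as per Section 8.2.7*.

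The cost is one phrase in one table cell. No test is added beyond those Section 8.2.7 already asks for, and the design, sample size and analysis do not change.
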